CLINICAL STUDY PROTOCOL

**A 6-Week, Randomized, Evaluator Blinded, in vivo
within Subject Repeat Test to Evaluate the Irritation and Sensitization Potential of OmezaTM
Collagen Matrix in Healthy Volunteers**

[figure not shown]
PCR Number: OMZRIP1F

Document Dates

Final Protocol: 29 October 2019

Sponsor

Omeza

Conducted By:

Princeton Consumer Research Corp.
[name]
[name]
[name]

PRINCIPAL INVESTIGATOR SIGNATURE SHEET

**A 6-Week, Randomized, Evaluator Blinded, in vivo
within Subject Repeat Test to Evaluate the Irritation and Sensitization Potential of OmezaTM
Collagen Matrix in Healthy Volunteers**

Protocol Number: OMZRIP1F

By my signature below, I attest that I have read, understood, and agree to abide by all conditions, instructions, and restrictions contained in this protocol (including appendices). I understand that any changes in the protocol must be approved in writing by Omeza and Princeton Consumer Research before they can be implemented, except where necessary to eliminate immediate hazards to the subject.

Approval Signature

Principal Investigator: _____ Date _____
Signature

[name].
Princeton Consumer Research
[name]
[name]
[name]

SPONSOR COMPANY SIGNATURE SHEET

**A 6-Week, Randomized, Evaluator Blinded, in vivo
within Subject Repeat Test to Evaluate the Irritation and Sensitization Potential of OmezaTM
Collagen Matrix in Healthy Volunteers**

Protocol Number: OMZRIP1F

By my signature below, I reviewed and approved this protocol (including appendices).

Reviewer Signature

Sponsor: _____ Date _____

Signature

[name]

Omeza

A block of three horizontal black bars of varying lengths, representing a redacted signature.

PROTOCOL SYNOPSIS**TITLE:**

**A 6-Week, Randomized, Evaluator Blinded, in vivo
within Subject Repeat Test to Evaluate the Irritation and Sensitization Potential of OmezaTM
Collagen Matrix in Healthy Volunteers**

PROTOCOL NUMBER:

OMZRIP1F

OBJECTIVES:

To assess the sensitization potential of OmezaTM Collagen Matrix compared to that of a negative control (0.9% sodium chloride, NaCl) using 9 consecutive continuous applications on the back area over a 3-week induction period, a 10-17-day rest period, and a challenge phase of approximately 48 hours exposure with evaluations over 72 (± 2) hours.

The secondary objective is to assess the safety of OmezaTM Collagen Matrix by monitoring adverse events throughout the study.

POPULATION:

A sufficient number of subjects will be qualified for the study to randomize approximately 60 subjects with the intention that a minimum of 50 subjects will complete the challenge phase.

STUDY DESIGN AND DURATION:

The study design is based on a Modified Draize Human Repeat Insult Patch Test. This is a single site, evaluator-blinded study using a within-subject randomized design. Each subject will receive all investigational products at the same time. The trained skin evaluator and Investigator will be blinded to the identity of the test materials. The investigational products will be OmezaTM Collagen Matrix and a negative control (0.9% aqueous sodium chloride). The study will involve repetitive and continuous patch applications of all investigational products to the same test sites on the back approximately 48 hours on weekdays and for approximately 72-hour periods over weekends over 3 weeks, for a total of 9 induction applications. Sites on the back area will be evaluated by the blinded trained evaluator after each patch removal. Subjects will have a rest period of 10 – 17 days, followed by challenged applications of each investigational product to naïve sites for approximately 48 hours. Evaluations of the challenge sites will be made at approximately 30 minutes, 24 (± 1), 48 (± 2), and 72 (± 2) hours post removal. The study will require 15 visits to the testing facility. Total study duration after screening will be approximately 5-6 weeks for each subject.

INCLUSION CRITERIA:

Subjects who have provided written informed consent and an authorization for disclosure of protected health information must meet the following criteria:

- a. Males and Females, age 18 to 65 years;
- b. Good general health, as assessed by medical history and brief dermal skin examination

- of the application sites (back);
- c. Fully informed of the risks of entering the study and willing to provide written consent to enter the study;
- d. Willing to follow study rules, which include: no sun exposure (for example; no swimming, sunbathing, or tanning beds), avoid activities that would cause excessive sweating, abstain from use of lotions, creams, or oils on the back area;
- e. Must be willing to not change current brand of personal care products such as soaps, body washes, laundry detergents, body sprays, body spritzes, etc. while participating on the study;
- f. Willing and able to practice an acceptable measure of contraception (i.e. birth control medication for at least 3 months prior, condom with spermicide or birth control injections,) during the study, if female of childbearing potential. To be considered female of non-childbearing potential, subject must of have had a hysterectomy, tubal ligation, or have been post-menopausal for at least 1 year.

EXCLUSION CRITERIA:

Subjects must be excluded if any of the following conditions exist:

- a. Clinically significant skin disease which may contraindicate participation, including psoriasis, eczema, atopic dermatitis, and active cancer;
- b. Asthma that requires medication;
- c. Insulin-dependent diabetes;
- d. Known immunological disorders such as HIV positive, AIDS and systemic lupus erythematosus;
- e. Treatment for any type of cancer within the last six months;
- f. Routine use (as defined by using more than 3 days in a week) of any anti-inflammatory drug (e.g., aspirin, ibuprofen, corticosteroids; 81 mg aspirin is acceptable), immunosuppressive drugs, antihistamine medication (steroid nose drops and/or eye drops are acceptable) or over-the-counter pain medication that is ingested in quantities exceeding label instructions;
- g. Use of topical drugs at patch site;
- h. Pregnancy, lactation, or planning a pregnancy (confirmed by urine pregnancy test administered to females of childbearing potential);
- i. Medical condition which, in the Investigator's judgement, makes the subject ineligible or places the subject at undue risk;
- j. Participation in any patch test for irritation or sensitization within the last four weeks;
- k. Dermatological aberrations in or around test sites which includes sunburn, extremely deep tans, uneven skin tones, tattoos, scars, excessive hair, numerous freckles or other disfigurement of the test site;
- l. Confirmed allergy to adhesives, bandages, or ingredients in OmezaTM Collagen Matrix;

m. History of anaphylaxis to matrix ingredients (e.g. fish, palm oil, hemp oil, beeswax).

DOSAGE FORMS AND ROUTE OF ADMINISTRATION:

- Investigational Product :

Approximately 0.2 ml of OmezaTM Collagen Matrix – Batch no. PVP8

- Control Product:

Approximately 0.2 ml of 0.9% aqueous NaCl

The patch system will be patch pads made from Webril® and affixed with an occlusive hypoallergenic tape, unless the skin condition becomes sufficiently irritated to require a change to a semi-occlusive tape or even an open dressing, at the discretion of the investigator. Additional tape may be used to ensure patches stay adhered to the test sites.

EVALUATION OF IRRITATION AND SENSITIZATION:

All subjects will be evaluated using the Skin Irritation Scale:

Inflammatory Responses:

0	=	No visible reaction
+	=	Slight, confluent or patchy erythema
1	=	Mild erythema (pink)
2	=	Moderate erythema (definite redness)
3	=	Strong erythema (very intense redness)

Definition of letter grades appended to a numerical grade:

E	=	Edema - swelling, spongy feeling when palpated
P	=	Papule - red, solid, pinpoint elevation
V	=	Vesicle - small elevation containing fluid
B	=	Bulla reaction - fluid-filled lesion (blister)
S	=	Spreading - evidence of the reaction beyond the Webril pad area
W	=	Weeping - result of a vesicular or bulla reaction - serous exudate
I	=	Induration - solid, elevated, hardened, thickened skin

Superficial Effects

g	=	Glazing
y	=	Peeling
c	=	Scab, dried film of serous exudate of vesicular or bulla reaction
d	=	Hyperpigmentation (reddish-brown discoloration of test site)
h	=	Hypopigmentation (loss of visible pigmentation at test site)
f	=	Fissuring grooves in the superficial layers of the skin

All skin responses observed with the investigational products during the induction and challenge phases will be reported. Skin responses to each patch application will be examined and graded under light supplied by a 100-watt incandescent blue bulb. The evaluator and Investigator will be blinded to treatment assignment and any previous scores. The same individual will conduct all skin evaluations of the test sites, but a qualified back-up individual will be available if needed.

Individual investigational products during the induction phase will be applied to the assigned

skin site unless the site reactions become so strong as to make it inadvisable. If excessive irritation, (for example, a numerical score of 2 or greater) is noted, that site will be discontinued from further patching and a new site adjacent to the original site will be used for the remainder of the required applications. If excessive irritation occurs at the move site, a second move site may be used. Excessive irritation at the second move site would require discontinuation of that investigational product.

The challenge patches will be applied to naïve sites on the opposite side of the back for approximately 48 hours. Challenge sites will be evaluated approximately 30 minutes, 24 (± 1), 48 (± 2) and 72 (± 2) hours after patch removal. Evaluation of the test articles for the potential to sensitize should include the site scores as well as a narrative description of any reaction and an opinion from the investigator as to whether the reaction is indicative of a contact sensitization.

Photos will be taken of any reactions of concern and will be shared with the sponsor but will not be part of the final report.

SAFETY ASSESSMENTS:

Safety will be assessed by monitoring of adverse events reported during the study.

STATISTICAL ANALYSES:

Data from the individual patch sites is presented in tabular format. No statistical analysis of the data will be performed.

SAMPLE SIZE DETERMINATION:

Based on prior experience with contact sensitization studies in humans approximately 60 subjects will be randomized to ensure 50 subjects completing the study. There is no statistical calculation of sample size for this study.

SITES:

This study will be conducted at 1 site located in the United States.

SPONSOR:

Omeza

TABLE OF CONTENTS

1	INTRODUCTION, RATIONALE, AND OBJECTIVES.....	10
1.1	Introduction.....	10
1.2	Rationale.....	10
1.3	Objectives.....	10
2	INVESTIGATIONAL PLAN.....	11
2.1	Overall Study Design	11
2.2	Randomization and Blinding Procedure	11
3	SELECTION AND WITHDRAWAL OF SUBJECTS	11
3.1	Inclusion Criteria.....	11
3.2	Exclusion Criteria.....	12
3.3	Subject Withdrawal Criteria	12
4	STUDY TREATMENTS	13
4.1	Identity of Test Products.....	13
4.2	Test Product Storage and Accountability.....	13
4.3	Methods of Assigning Subjects to Treatment Groups.....	13
4.4	Administration of Test Products.....	14
4.5	Treatment Accountability and Compliance	14
4.6	Blinding and Unblinding Method.....	14
5	SCHEDULE OF PROCEDURES AND ASSESSMENTS	14

1 INTRODUCTION, RATIONALE, AND OBJECTIVES

1.1 Introduction

1.2 Rationale

This study design has been selected by the sponsor to address comments provided by the FDA in order to aid in identifying and eliminating any potential irritants or sensitization in future product development and is based on a Modified Draize Human Repeat Insult Patch Test design. The Modified Draize Procedure¹ is used as a predictive test for contact sensitization in humans. The procedure involves the application of a discontinuous series of multiple occlusive patches to human skin over a three-week induction period. Induction is followed by an approximate two-week rest period. Challenge consists of a single application to naive skin.

¹Marzulli, F.N. and Maibach, H.I. (1977) Contact Allergy: Predictive Testing in Humans. In Advances in Modern Toxicology.

Dermatotoxicology and Pharmacology. Eds. Marzulli, F.N and Maibach, H.I. 4, 353-372.

1.3 Objective

To assess the sensitization potential of OmezaTM Collagen Matrix compared to that of a negative control (0.9% sodium chloride, NaCl) using 9 consecutive continuous applications on the back area over a 3-week induction period, a 10-17-day rest period, and a challenge phase of approximately 48 hours exposure followed by evaluations over 72 (± 2) hours.

The secondary objective is to assess the safety of OmezaTM Collagen Matrix by monitoring adverse events throughout the study.

2 INVESTIGATIONAL PLAN

2.1 Overall Study Design

This is an evaluator-blinded study using a within-subject randomized design. Each subject will receive all investigational products at the same time. The trained skin evaluator and Investigator will be blinded to the identity of the test materials. The investigational products will be OmezaTM Collagen Matrix liquid and a negative control (0.9% aqueous sodium chloride). The study will involve repetitive and continuous patch applications of all investigational products approximately 48 hours on weekdays and for approximately 72-hour periods over weekends over 3 weeks, for a total of 9 induction applications. Sites on the back area will be evaluated by the blinded trained evaluator after each patch removal. Subjects will have a rest period of 10 – 17 days, followed by challenged applications of each investigational product to naïve sites for approximately 48 hours. Evaluations of the challenge sites will be made approximately 30 minutes, 24 (± 1), 48 (± 2) and 72 (± 2) hours post removal. Total study duration after screening will be approximately 5-6 weeks for each subject.

2.2 Randomization and Blinding Procedure

To eliminate skin evaluator bias, the assignment of the test product codes to the subject's test sites will be randomized among the subjects so that each test product code (see section 5.1) occupies individual skin sites within the panel of test subjects with equal frequency. The randomization scheme will be provided by the site.

3 SELECTION AND WITHDRAWAL OF SUBJECTS

The study will enroll approximately 60 subjects to complete approximately 50 subjects.

Subjects will be healthy volunteers drawn from the general population following the inclusion and exclusion outlined below. Subjects withdrawn from the study before completion will not be replaced.

3.1 Inclusion Criteria

1. Males and Females, age 18 to 65 years;
2. Good general health, as assessed by medical history and brief dermal skin examination of the application site (back);
3. Fully informed of the risks of entering the study and willing to provide written consent to enter the study;
4. Willing to follow study rules, which include: no sun exposure (for example; no swimming, sunbathing, or tanning beds), avoid activities that would cause excessive sweating, abstain from use of lotions, creams, or oils on the back area;
5. Must be willing to not change current brand of personal care products such as soaps, body washes, laundry detergents, body sprays, body spritzes, etc. while participating on the study;
6. Willing and able to practice an acceptable measure of contraception (i.e. birth control

medication for at least 3 months prior, condom with spermicide or birth control injections,) during the study, if female of childbearing potential. To be considered female of non-childbearing potential, subject must of have had a hysterectomy, tubal ligation, or have been post-menopausal for at least 1 year.

3.2 Exclusion Criteria

1. Clinically significant skin disease which may contraindicate participation, including psoriasis, eczema, atopic dermatitis, and active cancer;
2. Asthma that requires medication;
3. Insulin-dependent diabetes;
4. Known immunological disorders such as HIV positive, AIDS and systemic lupus erythematosus;
5. Treatment for any type of cancer within the last six months;
6. Routine use (as defined by using more than 3 days in a week) of any anti-inflammatory drug (e.g., aspirin, ibuprofen, corticosteroids; 81 mg aspirin is acceptable), immunosuppressive drugs, antihistamine medication (steroid nose drops and/or eye drops are acceptable) or over-the-counter pain medication that is ingested in quantities exceeding label instructions;
7. Use of topical drugs at patch site;
8. Pregnancy, lactation, or planning a pregnancy (confirmed by a urine pregnancy test administered to females of childbearing potential);
9. Medical condition which, in the Investigator's judgement, makes the subject ineligible or places the subject at undue risk;
10. Participation in any patch test for irritation or sensitization within the last four weeks;
11. Dermatological aberrations in or around test sites which includes sunburn, extremely deep tans, uneven skin tones, tattoos, scars, excessive hair, numerous freckles, or any other disfigurement of the test site;
12. Confirmed allergy to adhesives, bandages, or ingredients in OmezaTM Collagen Matrix;
13. History of anaphylaxis to matrix ingredients (e.g. fish, palm oil, hemp oil, beeswax).

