5.6 Challenge Phase (Visit 12)

- Adverse event, concomitant medication review
- Patch removal
- Note: Approximate 30-minute wait time from removal to evaluation
- Skin evaluation
- Photograph(s) of sites if applicable

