6.8 Assessment of Sensitization

Subjects who had all 9 induction patches and completed the challenge phase (at least the 24-hour post challenge skin assessment) will be considered evaluable subjects for the study. The Principal Investigator in consultation with the irritation grader will review all induction and challenge scores recorded for all evaluable subjects. The induction of dermal sensitization is determined by enhancement of the skin reaction observed at Challenge greater than that observed during Induction. Low grade reactions observed during Induction, but which are not observed at Challenge are considered to be irritant in nature.

An erythematous and edematous reaction to the test article (and none to the negative control) during Challenge is indicative of dermal sensitization. Usually the skin irritation score response is greater than scores observed during induction phase and often spreads outside of the patch site. If sensitization is suspected, a full description of the skin responses observed will be documented and reported in the final report.

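### The day-count drug exclusion lets some users of systemic corticosteroids or immunosuppressive drugs enter, and 6.8 then counts them as evaluable negatives; probably uncommon, with a modest effect

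*Combined protocol and SAP*

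**What the plan says.** - **Entry (protocol 3.2, item 6).** The exclusion covers "Routine use (as defined by using more than 3 days in a week) of any anti-inflammatory drug (e.g., aspirin, ibuprofen, corticosteroids". The list continues, still governed by routine use, with "immunosuppressive drugs, antihistamine medication (steroid nose drops and/or eye drops are acceptable". Low-dose aspirin and steroid nose or eye drops are allowed. No route, washout or look-back period is given.
- **Synopsis, exclusion f.** The threshold is the same: "Routine use (as defined by using more than 3 days in a week) of any anti-inflammatory drug".
- **Study rules (3.1, item 4).** The rule begins "Willing to follow study rules, which include: no sun exposure" and goes on to sweating and to products put on the back. Item 5 concerns personal care brands. Neither mentions systemic medicines.
- **During the study (5.1 to 5.7).** Visit 1 records medicines for the past 30 days. The entry "Adverse event, concomitant medication review" appears at every later visit. Visit 11 adds an eligibility review, with no criteria of its own. No consequence of medicine use is stated.
- **Evaluability (6.8).** "Subjects who had all 9 induction patches and completed the challenge phase (at least the 24-hour post challenge skin assessment) will be considered evaluable subjects". Medication is not mentioned.
- **Analysis (7.2) and report (13.1).** Tabulation only. The listed report contents do not include concomitant medication.

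**The concern.** The evident purpose of item 6 is to keep out people whose medicines could mask a skin reaction. A count of dosing days may serve that purpose for an occasional painkiller. It serves it poorly for a systemic corticosteroid or immunosuppressive drug, where few dosing days need not mean little effect.

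The error has a direction. Under 6.8, sensitization is called when the challenge reaction exceeds the induction reaction, or when the test article provokes redness and swelling and the control does not. A subject whose response is suppressed tends to show neither and is tabulated as negative. The saline site cannot reveal this, because systemic suppression acts on both sites. The bias therefore favours a finding of no sensitization, which is the primary question.

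**Working it through.** **1. Apply the entry rule as written.** A subject is excluded only if use exceeds 3 days in a week.

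| Pattern of use | Days in a week | More than 3? | Result under item 6 |
|---|---|---|---|
| Corticosteroid, 3 days every week | 3 | No | Eligible |
| Immunosuppressive drug, once a week | 1 | No | Eligible |
| Immunosuppressive drug, every two weeks | 0 or 1 | No | Eligible |

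Corticosteroids are named inside the test, so the first row is unambiguous. The other two rest on the natural reading that routine use governs the whole list. Item 7, on topical drugs at the patch site, has no day count, so an exclusion without a threshold already exists in the same list.

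**2. Follow such a subject forward.** At Visit 11 an eligibility review can at most reapply the same threshold, and it comes before every challenge reading. A drug started after Visit 11 is recorded, but no rule acts on it. With 9 induction patches and the 24-hour challenge reading, the subject is evaluable. Without a reaction, the subject is an evaluable negative.

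**3. The plan's own figure.** The synopsis gives about 60 randomized for 50 completing and states that there is no statistical calculation, so there is none to reproduce. The implied loss is (60 − 50)/60 = 16.7%, and 50/(1 − 1/6) = 60. No stated figure depends on item 6.

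**4. Size, by illustration.** Suppose k of 50 evaluable subjects could not react at all. The documents give no value for k. The effective number is n = 50 − k.

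- Zero-reactor one-sided 95% upper bound on the sensitization rate: 1 − 0.05^(1/n).
- Chance of at least one reactor at an assumed true rate of 2%: 1 − 0.98^n.

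| k (assumed) | n | Upper bound, 0 reactors | Chance of at least 1 reactor at 2% |
|---|---|---|---|
| 0 | 50 | 5.8% | 63.6% |
| 2 | 48 | 6.05% | 62.1% |
| 5 | 45 | 6.4% | 59.7% |
| 10 | 40 | 7.2% | 55.4% |

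Total non-response is the worst case. Partial suppression would move these figures less.

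**5. Why exposed non-reactors alone should not be dropped.** Take 5 exposed subjects among 50, one of whom reacts, with no other reactors. The full set gives 1/50 = 2.0%. Removing only the 4 exposed non-reactors gives 1/46 = 2.2%. Removing all 5 gives 0/45. The middle figure chooses its denominator by outcome and is biased upward. Showing the first and last together is not selective.

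**The case against.** The strongest reply is that such subjects are unlikely to be in this panel. Section 3 calls for healthy volunteers. Section 3.1 requires good general health on medical history. Section 3.2 excludes psoriasis, eczema, atopic dermatitis, asthma needing medication, known immunological disorders and recent cancer treatment, and leaves other medical conditions to the investigator. A long-term immunosuppressive drug is taken for a condition, and that condition would have to pass all of these. During the study, 3.3 lets the investigator remove a subject when that seems advisable, and a subject removed before the 24-hour challenge reading is not evaluable.

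This stands as to frequency: the case is uncommon, and some mechanism exists. It does not close the gap. These criteria address conditions, not drugs. Withdrawal is optional and names no medicine. None of them covers a short corticosteroid course during the study.

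Three stronger readings are tempting, and the documents do not support them:

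- A reader might infer that a stated share of the negatives carries no information. No prevalence is given, and nothing suggests that several of 50 healthy volunteers would be affected.
- A reader might take 3 days in 7 (43%) as a measure of suppression. It is only a permitted dosing frequency.
- A reader might conclude that exposed negatives should leave the evaluable set. That is exclusion by outcome. Because withdrawn subjects are not replaced (3 and 4.3) and only about 50 are expected to complete, it could also take the panel below 50.

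**Conclusion.** The point holds as a defect of wording. Item 6 admits some of the people it is evidently meant to keep out, and 6.8 then counts their non-reactions, or those of subjects who take such a drug during the study, as ordinary negatives. The bias runs toward no sensitization.

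The number affected is unknown and the effect is probably modest. Even with 5 of 50 wholly unable to react, the zero-reactor bound moves from 5.8% to 6.4%, and the chance of seeing a reactor at a 2% rate falls from 63.6% to 59.7%. The conclusion assumes that systemic corticosteroids and immunosuppressive drugs can dampen the reaction being graded, which the exclusion itself implies, and that the day count governs the whole list. The 2% rate and the values of k are illustrative. The change is worth making because it is cheap and the error has a known direction. The study's conclusion should not be presumed wrong on this ground.

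**What to change.** 1. **Section 3.2 item 6 and synopsis item f.** Take systemic corticosteroids and immunosuppressive drugs out of the day-count test and exclude any current use. The sponsor should define the look-back period that makes use current; medicines for the past 30 days are already recorded at Visit 1. Keep the day count for the other listed drugs.
2. **Section 6.8.** Keep the evaluable set as defined. List every subject who used such a drug between the first patch and the last challenge reading, whatever the reaction, and report the sensitization result both with and without all of those subjects.

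The cost is a few more screen failures and one extra tabulation. The medication data are already collected, and no evaluable subject is lost from the main result.
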